10.1 Demographic Variables

The demographic variables collected in this study include age, gender (including childbearing potential for female subjects), race, and ethnicity. Subjects who record more than one race will be grouped into a single category denoted as multi-racial. Demographic variables will be summarized for the ITT and Safety populations, separately.

Age (years) will be summarized, overall and by treatment, using continuous descriptive statistics. Age will also be categorized as follows: <65 years and \geq 65 years. Age will be reported in years and calculated using the following formula:

Age = (Informed Consent Date – Date of Birth) / 365.25, truncated as an integer

The number and percentage of subjects will be presented, overall and by treatment, for age category, gender, race, and ethnicity.

A subject listing that includes all demographic variables will be provided.

10.2 Baseline Characteristics

[REDACTED]
[REDACTED]
[REDACTED] The following screening visit assessments will be summarized by study eye and all eyes using the appropriate set of statistics in the ITT population: [REDACTED]

[REDACTED] BCVA; [REDACTED] Eyelid Margin Redness Scale, Eyelid Debris Scale, [REDACTED], [REDACTED] slit lamp biomicroscopy eyelid, conjunctiva, cornea, lens, iris, pupil, and anterior chamber assessments; [REDACTED] IOP; and dilated ophthalmoscopy vitreous, retina, macula, choroid, and optic nerve assessments along with cup-to-disc ratio in the horizontal and vertical dimensions. Further details about these assessments are given later in the SAP.

A subject listing that includes all pre-treatment variables will be provided.

11 Medical History and Concomitant Medications

11.1 Medical History

Medical history will be coded using the Medical Dictionary for Regulatory Activities (MedDRA) version 22.0.

Non-ocular medical history will be summarized using discrete summary statistics and presented by treatment group at the subject and event level by System Organ Class (SOC) and Preferred Term (PT) using the ITT population. Ocular medical history will be similarly summarized at the subject level. If a subject reports the same PT multiple times within the same SOC, that PT will only be reported once within that SOC. As with the PT, if a subject reports multiple conditions within the same SOC, that SOC will only be reported once.

Listings of medical history will be generated separately for ocular and non-ocular data.

11.2 Concomitant Medications

Concomitant medications will be coded using World Health Organization (WHO) Drug Dictionary (Global B3, March 2019) and summarized to the therapeutic drug class (Anatomical Therapeutic Chemical [ATC] 4 classification) and preferred name. If the ATC 4 classification is not provided, the next lowest classification that is provided in the coding dictionary will be used. The preferred name will be defined as the active ingredient; if the active ingredient is not provided or includes more than two ingredients (e.g., multivitamins)

then the drug name will be summarized as the preferred name. Any uncoded terms will be summarized under the ATC classification and preferred name of “Uncoded.”

Concomitant medications are defined as those medications listed as having been taken (1) prior to initiation of study drug administration and continuing for any period of time following the first administration of study drug or (2) at any time following the first administration of study drug.

Concomitant medications will be summarized using the ITT population separately for ocular and non-ocular data. Medications will be tabulated for each treatment group using frequencies and percentages. Subjects may have more than 1 medication per ATC text. At each level of subject summarization, a subject will be counted once if he/she reports 1 or more medications. Percentages will be based on the number of subjects in each treatment group. Listings of prior and concomitant medications will be generated separately for ocular and non-ocular medications.

12 Dosing Compliance and Treatment Exposure

12.1 Dosing Compliance

Dosing compliance (% compliance) will be assessed by calculating the number of actual doses received and comparing that to the number of expected doses as follows:

$$\text{Compliance (\%)} = 100\% \times \frac{\text{Number of doses received}}{\text{Number of expected doses}}$$

The number of doses received will be determined through a review of the subject diary and the in-office applications. The number of expected doses is 14 for subjects assigned to Cohort 1 and 28 for subjects assigned to Cohort 2.

Dosing compliance (%) will be summarized with continuous descriptive statistics for each treatment group, using the ITT population. The compliance category defined above will be summarized with discrete summary statistics.

A subject listing of dosing compliance, including eyelid scrub data, will also be produced.

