Study Period	Q1-Q4 2019
Study Phase	Phase 2

Study Design	This is a multi-center, randomized, double-masked, placebo-controlled, dose-escalation Phase 2 study evaluating the safety and tolerability of NCX 4251 (fluticasone propionate nanocrystal) Ophthalmic Suspension 0.1% QD and BID for the treatment of acute exacerbations of blepharitis. The study will be performed in two sequential dose escalating cohorts.
Number of Subjects	This study will be conducted in approximately 3 to 5 sites in the United States. Approximately 50 subjects will be screened and approximately 35 will be randomized.
Study Objectives	The primary objective of this clinical study is to select the dose(s) of NCX 4251 to advance into the next stage of development. Secondary objectives of the study are to assess the safety and tolerability of the study medication applied QD and BID.
Selection of Target Subject Population	The target population in this study will be adult men and women with a documented history of blepharitis who are currently experiencing an acute exacerbation [REDACTED] at the Screening and Baseline/Day 1 Visits.
Study Medication, Comparator, Dosage and Mode of Application	Subjects will be randomized in a 2:1 ratio in Cohort 1, and in a 1:1 ratio in Cohort 2. Cohort 1 (two parallel groups): Approximately 10 subjects on NCX 4251 0.1% QD (Group A) Approximately 5 subjects on Placebo QD (Group B) Cohort 2 (two parallel groups): Approximately 10 subjects on NCX 4251 0.1% BID (Group C) Approximately 10 subjects on Placebo BID (Group D) Study medication will be applied via a sterile applicator to the upper and lower eyelid and lower eyelid margin of both eyes once daily in the morning (Cohort 1) or twice daily, in the morning and in the evening (Cohort 2), for 14 days. In addition, all subjects will perform daily morning eyelid scrubs of the upper and lower eyelids of both eyes using diluted baby shampoo applied with a cotton swab prior to the application of the study medication during the treatment period. Morning eyelid scrubs and application of study medication will be performed by the subject at the clinical site on the days of study visits. Morning eyelid scrubs will continue from study medication discontinuation until Day 28/Exit.

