3. STUDY DESIGN

3.1 Overall Study Design

This is a multi-center, randomized, double-masked, placebo-controlled, dose-escalation study. The four arms of the study will be conducted in two sequential dose escalating cohorts.

Screening of eligible subjects for Cohort 2 will commence once all Cohort 1 subjects have completed the Day 14 Visit [REDACTED]. An interim analysis will be performed following the completion of Cohort 1.

Subjects will be assessed for initial eligibility at the Screening Visit (Day -7 to -3). Eligible adult subjects with a history of blepharitis and who are experiencing an acute exacerbation of blepharitis [REDACTED]

[REDACTED] the Screening and Baseline/Day 1 Visits will be randomized into the study.

Subjects in Cohort 1 will be randomized in a 2:1 ratio to receive QD NCX 4251 Ophthalmic Suspension, 0.1% or placebo for application to both eyelids. Subjects in Cohort 2 will be randomized in a 1:1 ratio to receive BID NCX 4251 Ophthalmic Suspension, 0.1% or placebo for application to both eyelids.

Cohort 1

Group A: approximately 10 subjects on NCX 4251 Ophthalmic Suspension, 0.1% QD

Group B: approximately 5 subjects on Placebo QD

Study medication will be applied via a sterile applicator to the upper and lower eyelid and lower eyelid margin of both eyes QD [REDACTED] for 14 days. Subjects will also perform daily scrubs of the upper and lower eyelids of both eyes using diluted baby shampoo on a cotton swab prior to the application of the study medication.

Cohort 2

Group C: approximately 10 subjects on NCX 4251 Ophthalmic Suspension, 0.1% BID

Group D: approximately 10 subjects on Placebo BID

Study medication will be applied via a sterile applicator to the upper and lower eyelids and lower eyelid margin of both eyes twice daily [REDACTED] for 14 days. Subjects will also perform daily scrubs of the upper and lower eyelids of both eyes using diluted baby shampoo on a cotton swab prior to the morning application of the study medication.

For both Cohorts 1 and 2, study visits will be as follows: Screening (Day -7 to -3), Baseline/Day 1, Day 4 (\pm 1 day), Day 8 (\pm 1 day), Day 11 (\pm 1 day), Day 14 (- 1 day; last day of treatment), and Day 28/Exit (\pm 2 days; follow up visit).

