6.8 Study Medication Dispensing and Collection

For each subject fulfilling eligibility criteria and for each cohort, the clinical site staff will randomize subjects as per the randomization schedule [REDACTED] and provided to the site prior to the start of the study. A randomization number, which corresponds to a study medication kit number, will be allocated to each subject. [REDACTED]

The randomization and the study medication kit number must be allocated only on the day of the first treatment application during Baseline/Day 1. Replacement kit numbers will be provided by the Sponsor should a dispensed kit become lost or damaged.

Once all Baseline/Day 1 Visit study procedures have been completed, the site will dispense the study medication to the subject. Each subject will be given one kit [REDACTED]

Study medication will be dispensed by the Study Coordinator or another designated individual (other than the investigator(s)) at the study site.

Subjects will be instructed to return their study medication [REDACTED] to the Study Coordinator or another designated individual at the Day 14 Visit. An inventory will be conducted by the site.

Each subject will be given a copy of the study medication dosing and storage instructions.

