6.10 Instructions for Use and Application of Study Medication

The study medication must be administered to both eyelids each morning, [REDACTED], after eyelid scrubs (Cohort 1), or each morning, [REDACTED] after eyelid scrubs and each evening ([REDACTED]) (Cohort 2), from the Baseline/Day 1 Visit to Day 14 Visit.

[REDACTED]

Subjects must apply the study medication as instructed below using the supplies provided by the study site.

Study Medication Application Instructions

1. Wash your hands thoroughly with soap and water.

Preparation of study medication:

2. [REDACTED]

[REDACTED]

[REDACTED]

[REDACTED]

[REDACTED]

[REDACTED]

[REDACTED]

[REDACTED]

Now proceed with applying the study medication beginning with the right eye:

10. [REDACTED]

[REDACTED]

[REDACTED]

[REDACTED]

[REDACTED]

[REDACTED]

[REDACTED]

[REDACTED]

[REDACTED] applicator and tube, apply study medication to the left eye repeating Steps 2-16.

IMPORTANT! THE APPLICATOR SPONGE MUST NOT MAKE CONTACT WITH THE SURFACE OF THE EYE OR THE WHITE PART OF THE EYE. The only contact should be to the specified areas of the eyelid.

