16.2.2	Protocol Deviations
16.2.3.1	Inclusion/Exclusion Criteria
16.2.3.2	Analysis Populations
16.2.4.1	Demographics
16.2.4.2	Baseline Characteristics
16.2.4.3	Ocular Medical History
16.2.4.4	Non-Ocular Medical History
16.2.4.5	Prior and Concomitant Ocular Medications
16.2.4.6	Prior and Concomitant Non-Ocular Medications
16.2.5	Study Drug Administration
[REDACTED]	[REDACTED]

Listing Number	Title
16.2.7.1	All Adverse Events
16.2.7.2	Adverse Events Leading to Study Drug Discontinuation
16.2.7.3	Serious Adverse Events
16.2.7.7	Best Corrected Visual Acuity (BCVA) at 4 Meters (logMAR)
16.2.7.8	Intraocular Pressure (IOP)
16.2.7.9	Slit Lamp Biomicroscopy
[REDACTED]	[REDACTED]
16.2.7.11	Dilated Ophthalmoscopy
16.2.8	Urine Pregnancy Test

22 Appendix A

Table 1. Schedule of Visits and Assessments

	Screening Visit ^a (day -7 to -3)	Baseline/ Day 1 Visit	Day 4 Visit (± 1 day)	Day 8 Visit (± 1 day)	Day 11 Visit (± 1 day)	Day 14 Visit (- 1 day)	Day 28/ Exit Visit (± 2 days)
Informed Consent/HIPAA	X	-	-	-	-	-	-
Screening Number and Registration	X	-	-	-	-	-	-
Demographics	X	-	-	-	-	-	-
Medical/Ophthalmic History & Update	X	X	X	X	X	X	X
Concomitant Medications	X	X	X	X	X	X	X
Urine Pregnancy Test	X	-	-	-	-	X	-
	X	X	-	X	X	X	X
Best Corrected Visual Acuity (ETDRS)	X	X	X	X	X	X	X
Eyelid Evaluation	X	-	-	-	-	-	-
	-	X	X	X	X	X	X
Slit Lamp Biomicroscopy	X	X	X	X	X	X	X
	X	X	X	X	X	X	X
	X	X	-	-	-	-	X
	X	X	-	X	X	X	X
	X	X	-	X	X	X	X
IOP	X	X	X	X	X	X	X
	-	X	X	X	X	X	X
Study Medication Application	-	X ^c	X	X	X	X	-
	-	X ^d	X	X	X	X	X ^d
							X ^e
	X	X	-	-	-	X	-
Dilated Ophthalmoscopy	X	-	-	-	-	-	X
Inclusion/Exclusion Criteria	X	X	-	-	-	-	-
Randomization	-	X	-	-	-	-	-
Dispense study medication, study related material, diary and instructions	-	X	-	-	-	-	-
Review of subject diary	-	-	X	X	X	X	-
Collection of study medication and diary	-	-	-	-	-	X	-
Eyelid Scrub & Study Medication Application Training	-	X	-	-	-	-	-
Adverse Event Query	X	X	X	X	X	X	X
Study Exit	-	-	-	-	-	-	X

a) Screening Visit may be performed at any time of the day. All other visits will be performed in the morning with specific time points for certain assessments.

b) Daily eyelid scrubs will be performed prior to study medication application by the subject when self-administering study treatment. On study visit days eyelid scrubs and study medication application will be performed by the subject under the supervision of the study staff.

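### The 28 expected doses for Cohort 2 in SAP 12.1 cannot be reached on the readable schedule: a fully adherent BID subject seen on Day 14 can record at most 27 (96.4%)

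*SAP*

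**What the plan says.** SAP 12.1 defines compliance as doses received over doses expected, times 100. The denominator is fixed: "The number of expected doses is 14 for subjects assigned to Cohort 1 and 28 for subjects assigned to Cohort 2". The numerator has two sources: "The number of doses received will be determined through a review of the subject diary and the in-office applications".

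The regimen wording behind the denominator is in the protocol synopsis: "twice daily, in the morning and in the evening (Cohort 2), for 14 days". Protocol 3.1 describes the final treatment visit as "Day 14 (- 1 day; last day of treatment" and section 6.10 has dosing run "from the Baseline/Day 1 Visit to Day 14 Visit".

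The schedule is as follows:
- Protocol 7.2 and Appendix 4 place the first application at the Baseline/Day 1 visit, under supervision.
- Footnote a of SAP Appendix A, Table 1 (and of Protocol Appendix 1) says of the visits after Screening: "All other visits will be performed in the morning with specific time points for certain assessments".
- Protocol 7.5 has the subject apply the morning dose under supervision at Day 14. Site staff then collect the diary and the medication.
- Protocol 6.8 has subjects return their medication "to the Study Coordinator or another designated individual at the Day 14 Visit".
- In SAP Appendix A, Table 1, the row "Collection of study medication and diary" is marked at Day 14 only.

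**The concern.** The denominator follows the nominal regimen, while the numerator is limited by what the visit schedule lets a subject apply and record. For QD the two agree. For BID they differ by the evening application on Day 14, which on the readable text would have to be taken and written down after both medication and diary had been surrendered. The conflict lies within the SAP (12.1 against Appendix A) and also between the protocol's regimen wording and its collection step.

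What is at stake is the reading of the compliance summary (SAP section 20, Table 14.3.10). The study's primary objective is to choose the dose or doses to take forward, so readers will look at QD and BID adherence side by side. A shortfall built into the BID denominator can be mistaken for poorer adherence to twice-daily use.

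**Working it through.** **Inputs.** Treatment length 14 days and two applications a day in Cohort 2 (protocol synopsis). First application at the Day 1 visit (Protocol 7.2, Appendix 4). Last recordable application is the supervised morning one at the Day 14 visit (Protocol 7.5). Day 14 window of minus one day (Protocol 3.1). Expected doses 14 and 28 (SAP 12.1).

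**Reproducing the SAP's figures.** QD: 14 x 1 = 14. BID: 14 x 2 = 28. Both match.

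**Maximum recordable doses.** If the final treatment visit falls on day d and the last application is the supervised morning one:
- QD maximum = d
- BID maximum = 2 x (d - 1) + 1 = 2d - 1

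| Day of visit | QD maximum | QD compliance | BID maximum | BID compliance (SAP 12.1) |
|---|---|---|---|---|
| 14 | 14 | 14/14 = 100% | 2 x 13 + 1 = 27 | 27/28 = 96.4% |
| 13 | 13 | 13/14 = 92.9% | 2 x 12 + 1 = 25 | 25/28 = 89.3% |

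**Size of the gap.** At full adherence the QD minus BID difference is d/14 - (2d - 1)/28 = 1/28, or 3.6 percentage points, on either visit day. An early visit lowers both regimens but does not create or remove this gap.

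**Below full adherence.** A BID subject seen on Day 14 who misses one of the 27 recordable doses is reported as 26/28 = 92.9%, against 26/27 = 96.3% of what could be recorded.

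**Sensitivity to the Day 1 evening dose.** The count of 27 assumes it is taken at home. The kit is dispensed that day and no readable text omits the dose. If it were omitted, the maximum would be 26 and compliance 26/28 = 92.9%, so 27 remains an upper limit.

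**Could a later entry be recovered?** The diary-review row in both schedules ends at Day 14, and the Day 28 procedures in Protocol 7.6 contain no diary step. The closing instruction in Protocol 7.5 covers eyelid scrubs and contact lenses but no further medication, whereas the closing instructions in 7.2 to 7.4 do mention it.

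**The case against.** The strongest objection is redaction. Text is blacked out in the return instruction (Protocol 6.8), around the evening timing and just after the dosing span (6.10), after the supervision sentence (7.5) and in the evening instruction of Appendix 4. A provision for the last evening application could sit there. This stands as a limit on confidence. It does not overturn the point, because the lines on collecting medication and diary at Day 14 are readable in Protocol 7.5 and in both schedules.

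Second, 28 is correct arithmetic for the stated regimen, and a fixed planned-course denominator is a legitimate convention. Both are true. The fault is an inconsistency between the regimen wording and the collection step, which leaves the convention attainable for QD and unattainable for BID.

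Third, the contrast of 96.4% with 100% applies only to subjects seen on Day 14, and a denominator of 27 would still give 25/27 = 92.6% to an adherent BID subject seen on Day 13. That is so, but the one-dose gap between regimens is the same on Day 13. Conversely, a subject rescheduled past Day 14 under Protocol 7.2 might record 28 or more, but such a visit falls outside the minus-one-day window.

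Fourth, the consequence is small. The cohorts are sequential and not randomized against each other, placebo BID shows the same ceiling, and exposure in days is calculated separately (SAP 12.2). This is accepted and is why the point is rated minor.

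**Conclusion.** The point holds, as a minor one with moderate confidence. On the readable schedule, SAP 12.1 expects one more Cohort 2 dose than a fully adherent subject seen on Day 14 can record: 27 of 28, a shortfall of 1/28 = 3.6 percentage points, against none for QD.

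This rests on three assumptions: the redacted text contains no provision for taking and recording a Day 14 evening application, the subject is seen on Day 14, and the Day 1 evening dose is taken.

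The effect is confined to descriptive compliance. Efficacy results do not change, both Cohort 2 arms share the denominator, and no stated rule ties compliance to dose selection. SAP 12.1 refers to a compliance category, but no cut-off is readable there, so it cannot be said whether any subject would change category.

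**What to change.** Reconcile three places: the 14-day BID wording (protocol synopsis and section 3.1), the Day 14 collection of medication and diary (Protocol 6.8, 7.5 and Appendix 1; SAP Appendix A), and the expected count in SAP 12.1. Which number of applications is intended is for the sponsor to state; no view is taken here.

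Then set the Cohort 2 denominator to the number of applications that the reconciled schedule lets a fully adherent subject take and record. That is 27 if the readable schedule stands, and 28 only if the reconciled text provides for a second, recorded application on Day 14. Whether to adjust the denominator for a visit on Day 13 is the sponsor's choice, since a fixed planned-course count is acceptable.

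The cost is one reconciling sentence and, depending on the outcome, either one number in SAP 12.1 or one line on when medication and diary are collected. No new data are needed.

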12.2 Treatment Exposure

Extent of treatment exposure for completed or discontinued subjects will be calculated in days using the following:

$$\text{Extent of Exposure (days)} = (\text{Date of Last Dose} - \text{Date of Baseline/Day 1 Visit}) + 1$$

Extent of treatment exposure for subjects who were lost to follow-up will be calculated in days using the following:

$$\text{Extent of Exposure (days)} = (\text{Date of Last Recorded Visit} - \text{Date of Baseline/Day 1 Visit}) + 1$$

A subject listing of treatment exposure will be produced.

13 Efficacy Analyses

All assessments will be conducted by the Study Eye [REDACTED]

[REDACTED]

[REDACTED]

[REDACTED]

[REDACTED]

[REDACTED]

[REDACTED]

[REDACTED]

[REDACTED]

13.2 Efficacy Endpoints

The efficacy endpoints [REDACTED] will be evaluated with respect to the Study Eye, [REDACTED]

• [REDACTED]

• [REDACTED]

• [REDACTED]

The following endpoints will be evaluated with respect to the Study Eye [REDACTED]

[REDACTED]

• [REDACTED]

[REDACTED]

• Mean change from baseline in Composite (Sum) Score of Eyelid Margin Redness, Eyelid Debris, and Eyelid Discomfort

• [REDACTED]

[REDACTED]

• [REDACTED]

[REDACTED]

• [REDACTED]

[REDACTED]

• [REDACTED]

[REDACTED]

13.3 Eyelid Assessments

13.3.1 EYELID DISCOMFORT

[REDACTED] Eyelid Discomfort is subject-reported based on a four-point scale with responses of 0 = No eyelid discomfort, 1 = Mild [REDACTED] [REDACTED], 2 = Moderate [REDACTED] [REDACTED], [REDACTED], and 3 = Severe [REDACTED] [REDACTED].

13.3.2 EYELID MARGIN REDNESS

After assessing eyelid discomfort, the Investigator assesses and grades eyelid margin redness based on the following scale: 0 = None: [REDACTED] 1 = Mild: [REDACTED]

2 = Moderate:
and 3 = Severe: [REDACTED]

13.3.3 EYELID DEBRIS

After accessing eyelid discomfort and eyelid margin redness, the Investigator assesses and grades eyelid debris based on the following scale: 0 = None: [REDACTED] 1 = Mild: [REDACTED]
[REDACTED] 2 = Moderate: [REDACTED] 3 = Severe: [REDACTED]
[REDACTED]

13.3.4 COMPOSITE SCORE OF EYELID MARGIN REDNESS, EYELID DEBRIS, AND EYELID DISCOMFORT

The composite score of Eyelid Margin Redness, Eyelid Debris, and Eyelid Discomfort is defined as the sum across the three measurements at a particular visit. If any of the assessments is missing, the composite score will be set to missing.

